4 TRIAL DESIGN

This is a prospective, three-part (see Figure 1) open label, Phase I/II dose-finding and separate cohorts expansion trial to determine the safety, tolerability and efficacy of CLEVER-1 antibody FP-1305 in subjects with cutaneous melanoma, pancreatic ductal adenocarcinoma, ovarian cancer, colorectal adenocarcinoma, hepatocellular carcinoma, gallbladder cancer, cholangiocarcinoma, uveal melanoma, gastric (including GE junction) adenocarcinoma, ER+ breast cancer and anaplastic thyroid cancer. The enrolment period for Part I lasted for 13 months. It is estimated that the enrolment period for both Part II and III would be 24 months for either part. For each subject, the trial will consist of a screening period (maximum 28 days), treatment phase with FP-1305 (one year with potential to continue longer), and a post-treatment period for safety assessment (maximum 4 weeks). Survival data will be collected beyond the subject's active participation in the trial. The collection of the survival data of a subject is limited to 2 years from the first IMP dose (at 1 year and 2 years after the first IMP dose). The maximal total duration of the trial is estimated to be 6 years. In case it would be beneficial for a study subject to continue the treatment beyond one year (as judged by an investigator), the treatment can be continued within this protocol and the survival data will be collected for 1 year after the last IMP dose (see [8.7.1](#)).

Part I of the trial will involve the identification of tolerable doses amongst four predefined doses. This will be based on the occurrence of DLTs with an acceptable (target) DLT rate of 20%. It is estimated that in total 30 subjects in 2-4 countries will be accrued from all disease groups to be investigated. The highest dose that can be tolerated based on the target (maximum tolerated dose) will first be determined using an efficient, adaptive dose-finding design, a modified time-to-event continual reassessment method (TITE-CRM), which allows for more accurate determination of the highest tolerated dose and shorter trial duration than conventional dose-finding designs. An early stopping rule will be incorporated to allow the trial to stop early or insert a lower dose if there is an unacceptable level of DLT at the lowest dose (level 0; 0.3 mg/kg). The lower reserve dose levels are 0.1 mg/kg and 0.05 mg/kg as shown in [Table 4](#). The de-escalation reserve dose levels will be utilised if there is strong evidence to suggest that the MTD is lower than 0.3 mg/kg and may be utilised also if more data on safety, PK and/or PD markers is required for dose selection for Part II. The 20 mg/kg dose may be utilized based on MTD or receptor occupancy and other PD markers.

The decision on the number and timing of the doses via intravenous infusion was guided by nonclinical studies. The initial FP-1305 dose level (Dose Level 0; [Table 4](#)) is 0.3 mg/kg every

three weeks. For further dosing see also **Table 4**. The full DLT assessment period is 63 days (9 weeks) for each subject from the first dose in Part I. If a subject misses a dose during the DLT period, the period is not changed, but stays as nine weeks from the first dosing. Based on the preclinical data it is expected that the selected doses will be well-tolerated.

Table 4: Dose levels in Part I of the trial

Dose Level	Dose (mg/kg)
-2 (reserve)	0.05
-1 (reserve)	0.1
0	0.3
1	1
2	3
3	10
4 (reserve)	20

The primary objective of the Part I of the trial is to select an optimal, biologically/ immunologically active dose that will be used in Parts II and III of the trial. Additional doses 30-100 mg/kg are included to be investigated in Part II.

In Part I, the initial design of the two-stage TITE-CRM has been chosen such that subjects will be recruited in cohorts of 2. If a subject is withdrawn/discontinued for any reason or dies during Cycle 1 (i.e. within the first three weeks after the first IMP) at the first level (Level 0), the withdrawn/discontinued subject needs to be replaced and a new subject will be enrolled to the same dose level until two subjects have reached the three-week follow-up and the dose escalation to the second level may occur. Dose-escalation will occur (where possible) if no DLTs have been observed in the first two subjects, each of them with a minimum of three-week follow-up at given dose level 0. In the interest of safety, a single subject will be treated first when a new dose level is to be investigated. There is a minimum waiting period of 3 weeks prior to the recruitment of the next subject at any dose level. This initial design allows a simple and rapid escalation scheme (whilst still ensuring safety) in the absence of DLT. Subjects are continually monitored for the occurrence of DLT till 9 weeks (full DLT assessment period). The accumulated information from each subject will continually be used to guide dose decisions. Once a DLT is observed, the second stage commences and the TITE-CRM model is utilised to determine the next best estimate of the MTD, taking into account all the accumulated complete (9 weeks) and partial DLT information (< 9 weeks) of the treated subjects. The model will be updated as soon as it is feasible, for instance, after 1 or 2 subjects. In the TITE-CRM paradigm, at the point of dose-update, subjects who have started treatment but have not completed their full DLT assessment and have not experienced DLT are included in the probability calculation with a weight equal to the proportion of the full DLT assessment period they have completed. For instance, Subject X who had no DLT up to 4.5 weeks will be given a weight of $4.5/9=0.5$. Subjects who experienced DLT within the assessment period or complete the full assessment period are assigned full weight (Cheung et al. 2000).

Two subjects as minimum will be assessed at each dose level if no DLT occurs. The TITE-CRM will continually re-estimate the MTD during the DLT assessment period and accumulated information will be used to determine tolerable doses. Once six evaluable subjects are treated at first three dose levels for the full DLT assessment period and two subjects are treated at the fourth dose level for

minimum of three weeks, the Data Monitoring Committee (DMC) evaluates whether reserve doses are required before the dose for Part II can be selected. If deemed necessary, reserve dose(s) will be utilised. In addition, three additional subjects per dose level may be enrolled to any tested dose level to gather more data. If subjects are allocated to two or more dose levels in Part I, randomisation to the selected doses will be utilized.

The decision of using more dose levels will be made by the DMC on the basis of the data collected from the subjects. It is estimated that approximately 30 evaluable subjects in total in Part I will be enrolled. At the end of Part I, the DMC utilises the receptor occupancy, changes in immune function, PK, PD and/or ORR data to determine the dose or doses for further investigation in Part II. Further decisions about Part II dose levels can be made based on cumulative data collected throughout the study.

In addition, the DMC may also recommend to include additional subjects on certain dose levels to ensure sufficient data is available for optimal dose selection for the Part II.

Subjects with HCC may potentially exhibit decreased antibody (FP-1305) clearance, due to a possibility that the liver endothelium's lysosomal compartment is diseased. Based on investigators best decision, and consultation of Medical Monitor, the first subject enrolled with HCC during Part I or in Part II may be administered with a dose one level lower than the highest tested dose or the phase II recommended dose. In Part II the first subject with HCC and underlying liver cirrhosis may be administered one level lower than the recommended dose level for the first dose. The recommended dose should be administered from the second dose (Cycle 2) forward if no toxicity appeared. After this, additional subjects with HCC that are enrolled should be dosed at the recommended dose level, if no toxicity has appeared for the first subject with HCC during the first cycle of treatment (3 weeks) with the lower dose level.

Part II of the trial will involve expansion groups of subjects by tumour type. The following tumour types will be selected for cohort expansion after the data of the first part of the trial has been reviewed: advanced hepatocellular carcinoma, cholangiocarcinoma and gallbladder cancer, pancreatic ductal adenocarcinoma, ovarian cancer, colorectal adenocarcinoma, cutaneous melanoma, uveal melanoma, gastric adenocarcinoma (including GE junction), ER+ breast cancer and anaplastic thyroid cancer. Each cohort will contain 10 subjects in Part II (10 at each dose level with random allocation within the same dosing schema Q3W, Q2W or Q1W. In addition, new dose level(s) 30 mg/kg and possibly also 45 and 100 mg/kg that include more than one tumour type will be tested for tolerability and safety. The data from both Part I and Part II will be used to define CLEVER-1 positivity in each tumour type. In Part III, subjects will be enrolled in tumour types that have demonstrated preliminary anti-tumour activity based on the CBR. Up to a total sample size of 700 subjects in all parts will be enrolled in approximately 20-30 sites in 5-8 countries. Subjects in Part III are stratified by disease type as in Part II and may be stratified by CLEVER-1 positivity. In Part II and Part III, cohorts for a particular tumour type may be opened sequentially or not opened at all i.e., if there is a strong signal for efficacy in cutaneous melanoma, that cohort may be opened first. Each cohort of subjects with a certain tumour type will be analysed for efficacy after 10 subjects have been treated with the dose(s) selected for Part II. The decision of continuing the cohort for Part III will be based on the results obtained from this analysis supported by the statistical rule to continue the cohort. Cohorts with best efficacy signal at any dose level may be advanced to Part III. However, it may not be meaningful to advance all Part II cohorts at any dose level with a minimal and clinically not meaningful signal of efficacy into Part III.

Figure 1A displays the trial pathway including dose escalation and expansion phases. **Figure 1B** displays how the initial design of the TITE-CRM will work in the absence of any DLT in Part I. Once a DLT is observed, subsequent dose decisions will be made with the usage of the TITE-CRM. This will take into account all accumulated DLT information—both partial (<9 weeks) and complete (9 weeks).

In this study protocol, the study drug is administered Q3W intervals. Based on the analysis of the PK, receptor occupancy and PD during the Q3W administration, it was deemed necessary to study more frequent dosing. With Protocol Addendum, Q2W and Q1W dosing intervals are implemented into Part II and possibly also to Part III if deemed appropriate. The purpose is to investigate the tolerability, safety, PD and preliminary efficacy of more frequent dosings infusion (Q2W and Q1W). Scientific justification and details of conducting of Q2W and Q1W dosings have been presented in the FP-1305 Investigator's Brochure and Protocol Addendum, respectively

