15.7 Power Calculations

The operating characteristics of the TITE-CRM will be assessed to assure the design is well calibrated for determining the MTD. Fine-tuning of the model to tailor to the trial's requirements will be aided with the use of the Dose-Transition Pathways, which maps out in advance how the model will recommend doses for all permutations of DLT outcomes for the initial subjects (Yap et al, 2017). Details of the TITE-CRM is presented in the corresponding statistical analysis plan. Part II and Part III are based on adaptive Simon's Two-Stage design, with the following assumptions Type I error rate (α ; one-sided) 0.05, power 0.80, response probability in the palliative treatment 5% (alternative option for these subjects) and response in the trial treatment 20%, 10 subjects in each cohort with at least one subject that demonstrates clinical benefit (CBR by RECIST 1.1 criteria) in the Part II is needed to conclude that the cohort may be expanded. Additionally, data from Part II will be used to determine CLEVER-1 positivity in each of the cohorts. If it is possible that cohorts can be divided in

the CLEVER-1 positive and CLEVER-1 negative groups, both subgroups will be expanded in Part III so that 10 subjects in each group are recruited. In case there are 10/10 non-responders in either of the subgroups, then the recruitment will continue only in the other subgroup with responders. The recruitment can continue within that subgroup until the planned maximum of 29 subjects (or until the required 4 subjects that demonstrate clinical benefit are reached). If the subgroups cannot be defined, the Part III continues with the original cohorts having 1 responder in the cohort. In case there are clearly more negative than positive subjects in some cohort, and also clear difference in the response, the DMC will evaluate the data and decide further cohort expansions.

If the desirable response is obtained in Part III of the trial the cohort(s) may be further expanded.

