- To assess the overall survival in trial subjects who receive at least 1 dose of FP-1305
- To measure cytokine and chemokine concentration in peripheral blood
- To measure the immune cell profile in circulation
- To assess if treatment elicits a change in LDH, LDL and oxLDL, CRP, CA-125 (OC subjects), CA19-9 (PDAC, gallbladder cancer, cholangiocarcinoma, gastric adenocarcinoma subjects), AFP (HCC subjects), CEA (CRC, ER+ BC, gastric adenocarcinoma subjects), CA-15-3 (ER+ BC subjects) levels or other relevant markers pre- and post-treatment

4 Design and type of the study

This is a prospective, three-part (see [Figure 1](#)) open label, Phase I/II dose-finding and separate cohorts expansion trial to determine the safety, tolerability and preliminary efficacy of repeated doses of CLEVER-1 antibody FP-1305 administered in three-weeks intervals (Q3W) in subjects with cutaneous melanoma, pancreatic ductal adenocarcinoma, ovarian cancer, colorectal adenocarcinoma, hepatocellular carcinoma, gallbladder cancer or cholangiocarcinoma, uveal melanoma, gastric (including GE junction) adenocarcinoma, ER+ breast cancer and anaplastic thyroid cancer.

In Part I 30 subjects were enrolled as planned. Part II consists of 10 enrolled subjects per cancer type (10 disease cohorts) at each selected Part II dose (1 mg/kg for all cohorts and 0.3 mg/kg, 1.0 mg/kg and 3.0 mg/kg for colorectal adenocarcinoma cohort) and dosing scheme (Q3W for all cancer types, Q2W and Q1W for selected cancer types). In addition to these, the study recruited cohorts for Q3W dosing of 3.0 mg and 10.0 mg for Cutaneous melanoma and Gastric adenocarcinoma, and also a cohort testing a higher dose (30.0 mg/kg) for any cancer cohort. Part III additional subjects will be enrolled based on the continuation rules set in the protocol (cohorts with at least 1/10 Clinical Benefit Rate will be expanded to total of 29 evaluable subjects). Thus, it is estimated that the total number of subjects in the whole trial can be up to 700 enrolled subjects.

In the study protocol, the study drug is set to be administered Q3W intervals. Based on the analysis of the PK, receptor occupancy and pharmacodynamic during the Q3W administration, it was deemed necessary to study more frequent dosing. With a country specific addendum, Q2W and Q1W dosing intervals are implemented into Part II. These are evaluated as separate Part II expansion cohorts.

[figure not shown]

Figure 1. Study design

5 Study variables

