- The proportion of lymphocyte subsets (CD4, CD8, their ratio, NK-cells, B-cells and regulatory T-cells), and plotted against the scheduled sampling time. The level of circulating cytokines and chemokines (including but not necessarily limited to IFN γ , IL-1 β , IL-2, IL-4, IL-6, IL-8/CXCL8, IL-10, IL-12p70, IL-13 and TNF alpha, IP-10/CXCL10, Eotaxin/CCL11, MCP-1/CCL2, MIP-1 α /CCL3, MIP-1 β /CCL4) will be analysed by multiplex assays prior to and during the treatment.
- LDH, LDL, oxLDL, and CRP, as well as the following tumour specific markers CA-125 (OC subjects), CA19-9 (PDAC, gallbladder cancer, cholangiocarcinoma, gastric adenocarcinoma subjects), CEA (CRC, ER+ BC, gastric adenocarcinoma subjects), AFP (HCC subjects), CA-15-3 (ER+ BC subjects) levels prior to and during the treatment will be measured from blood.

6 Sample size considerations

In Part I 30 subjects were enrolled, in Part II up to 10 subjects in each selected Part II cohort (cancer type, dose level and dosing scheme) will be enrolled; in addition, testing of higher doses (30-100 mg/kg) in cohorts with multiple cancer types will proceed in parallel with the treatment of other Part II cohorts. In Part III additional subjects will be enrolled based on the continuation rules set in this protocol. Subjects are enrolled into a specific part of the study and continue in that part until they discontinue (i.e. subjects do not proceed from one part to the next part). It is estimated that the total number of subjects in the whole trial is up to 700.

7 Statistical hypotheses

Expansion of each cohort to Part III of the trial is based on the predefined rule applying Simon's 2-stage design. Clinical benefit ratio (CBR) of 1/10 is needed in order to expand the cohort up to a total of 29 subjects per cohort.

8 Analysis datasets

Following analysis populations have been described in the protocol:

Safety population: Includes all subjects who have received any amount of FP-1305. This formulates the Full Analysis Set for Safety (FAS-S).

DLT evaluable population: Includes all subjects in Part I who have received at least one dose of FP-1305 and followed up for at least three weeks. Any subject that withdraws, discontinues from the trial or dies not related to treatment prior to the end of the 9-week DLT assessment period will be replaced.

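### In colorectal, cutaneous melanoma and gastric cancer, the 0.05 alpha holds per dose cohort; if the best of three doses advances with its ten Part II subjects counted, the tumour-type false-positive rate is about 0.11

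*Protocol*

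**What the plan says.** - **Design figures.** Protocol 15.7 sets one-sided alpha at 0.05 and power at 0.80, with "response probability in the palliative treatment 5% (alternative option for these subjects) and response in the trial treatment 20" per cent. The first-stage gate is "10 subjects in each cohort with at least one subject that demonstrates clinical benefit". The final rule is four subjects with clinical benefit by a maximum of 29.
- **Unit of the rule.** Protocol 1.2 and SAP Part II section 6 define a Part II cohort by cancer type, dose level and dosing scheme. SAP Part II section 9 applies the Simon rule to each cohort on its own.
- **Counting.** SAP Part II section 7: "Clinical benefit ratio (CBR) of 1/10 is needed in order to expand the cohort up to a total of 29 subjects per cohort". Section 4 of that SAP also speaks of a total of 29. The ten Part II subjects are therefore inside the final count, and 19 are added.
- **Doses per tumour type.** SAP Part II section 4 gives 1 mg/kg for every tumour type and 0.3, 1 and 3 mg/kg for colorectal. It adds that "the study recruited cohorts for Q3W dosing of 3.0 mg and 10.0 mg for Cutaneous melanoma and Gastric adenocarcinoma" (read here as mg/kg). Colorectal, cutaneous melanoma and gastric thus have three Q3W doses each. Q2W and Q1W went to selected cancer types that the section does not name.
- **Selection.** Protocol section 4: "Cohorts with best efficacy signal at any dose level may be advanced to Part III".
- **Unit of the Part III conclusion.** Protocol 3.7 sets the objective in selected tumour types at a selected dose. Protocol 3.10 and 15.3.3 report Part III by tumour type, whereas Part II (15.3.2) is reported by tumour type and dose.

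**The concern.** The two parts use different units. The error rate is fixed for one dose cohort named in advance. The Part III statement is about a tumour type, at a dose that may have been picked because its first ten subjects did best, and those same ten then count towards the four successes. Neither document says what the choice does to the error rate. A reader who takes 0.05 as the chance of calling an inactive tumour type promising would be relying on a figure that is too low for any type tested at several doses. The pooled Part III rate would also be biased upwards, because ten of its 29 subjects were selected on the outcome.

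**Working it through.** **Inputs.** Null rate 5%, alternative 20%, gate ≥1/10, final ≥4/29 (Protocol 15.7); 19 added subjects (29 − 10, SAP Part II sections 4 and 7); K = 3 Q3W doses (SAP Part II section 4).

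**1. The plan's own figure.** With X ~ Bin(10, p) and Y ~ Bin(19, p):

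α = Σ over x ≥ 1 of P(X = x) · P(Y ≥ 4 − x)

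At p = 0.05:

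| x | P(X = x) | P(Y ≥ 4 − x) | product |
|---|---|---|---|
| 1 | 0.3151 | 0.0665 | 0.0210 |
| 2 | 0.0746 | 0.2453 | 0.0183 |
| 3 | 0.0105 | 0.6227 | 0.0065 |
| ≥4 | 0.0010 | 1 | 0.0010 |

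The sum is 0.0468. The same sum at p = 0.20 is 0.801. The stated alpha and power reproduce.

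**2. Best of K doses, ten subjects kept.** Let M be the largest of K independent Bin(10, p) counts, so P(M = m) = F(m)^K − F(m − 1)^K, with F the Bin(10, p) distribution function. At p = 0.05, F(0) = 0.5987, F(1) = 0.9139, F(2) = 0.9885 and F(3) = 0.9990. For K = 3:

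| m | P(M = m) | P(Y ≥ 4 − m) | product |
|---|---|---|---|
| 1 | 0.5486 | 0.0665 | 0.0365 |
| 2 | 0.2027 | 0.2453 | 0.0497 |
| 3 | 0.0310 | 0.6227 | 0.0193 |
| ≥4 | 0.0031 | 1 | 0.0031 |

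The sum is 0.1086; a simulation of 2 million runs gave 0.1089. For K = 2 the same formula gives 0.082. The chance that at least one dose passes the gate is 1 − 0.5987^K: 40% for K = 1, 64% for K = 2 and 79% for K = 3.

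**3. Every passing dose advances.** The chance that at least one of three doses reaches 4/29 is 1 − (1 − 0.0468)³ = 0.134.

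**4. If the ten did not count.** With 29 new subjects in Part III, the rate for K = 3 is 0.785 × P(Bin(29, 0.05) ≥ 4) = 0.785 × 0.0548 = 0.043. The increase comes from choosing a dose and then reusing its subjects.

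**5. Bias in the pooled rate, true rate 20% at every dose.** The mean first-stage count given that the gate is passed is 2.24 for one cohort and 3.08 for the best of three. Adding 19 × 0.20 = 3.8 expected among the new subjects, with all 29 enrolled:
- one unselected cohort: (2.24 + 3.8)/29 = 20.8%
- best of three: (3.08 + 3.8)/29 = 23.7%

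The gate alone adds 0.8 points. Choosing the best of three adds a further 2.9.

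**The case against.** The strongest reply is that the stated alpha is not breached. The rule is set and applied per cohort, and a cohort is one tumour type at one dose and schedule. Leaving some cohorts behind cannot raise the error of any given cohort above 0.047, and neither document claims 0.05 per tumour type. This stands. A reader might infer that the trial's actual alpha is 0.11 and the stated one is wrong, but the documents do not support that. The 0.11 is a different quantity, relevant because Part III is framed and reported by tumour type.

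A reader might also infer that the problem runs through the whole trial. It does not. Three Q3W doses are documented for three of the ten disease cohorts, and the other seven have one Q3W dose. How many Q2W or Q1W cohorts any type has cannot be read from the SAP's design section.

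The selection wording is plural and permissive, so advancing exactly one best dose is a scenario and not a rule. The SAP lists the extra melanoma and gastric cohorts as additions, so a simultaneous choice among three is not established there. This also stands. It does not bring the figure back to 0.047, however, since letting every passing dose advance gives 0.134.

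The protocol is less explicit than the SAP on counting. Section 15.6 speaks of 29 evaluable subjects, and the CLEVER-1 route in 15.7 recruits ten per subgroup in Part III. No Part III SAP is among the documents. With 29 new subjects the increase would vanish (0.043), but the SAP text that exists says a total of 29.

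Finally, the SAP calls its analyses exploratory, and going without multiplicity control across dose cohorts in a Phase I/II trial is defensible. That is a reason to leave the threshold alone. It is not a reason to leave the error rate of the Part III conclusion unstated.

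**Conclusion.** The point holds in a limited form. For colorectal, cutaneous melanoma and gastric cancer, 0.05 (exact 0.047) describes a single pre-specified dose cohort. It does not describe a tumour-type conclusion reached after choosing among three doses and reusing the chosen ten subjects. That rate is about 0.11 if the best dose advances and 0.134 if all passing doses do. The figures assume independent cohorts, a true rate of 5% at every dose and the SAP's counting of the ten Part II subjects. Types with a single regimen stay at 0.047. The pooled estimate carries a modest upward bias: 23.7% on average at a true 20%, against 20.8% for an unselected cohort that passes the gate. The defect is an unstated operating characteristic and a biased estimate; the two-stage rule itself is sound.

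**What to change.** 1. In Protocol 15.7 and SAP Part II section 7, state that alpha 0.05 applies per dose/schedule cohort. Beside it, give the tumour-type false-positive rate for the number of cohorts actually opened in that type: 0.082 for two and 0.109 for three when the best one advances. Name the assumptions, including that the ten Part II subjects count. If several doses may advance, give that figure as well (0.134 for three).
2. Where a dose was chosen among several, report the Part III ORR, CBR and irORR from the newly enrolled subjects alone, beside the total of 29.

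The cost is wording and one extra set of estimates, with no extra subjects. The stated error rate becomes less favourable for three tumour types. The new-subject interval is wider: with 19 in place of 29 subjects, by a factor of roughly √(29/19) = 1.24 at the same observed rate. The 4/29 threshold can stay as it is.
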